Antibody to diphtheria toxoid, tetanus-toxoid, pertussis toxoid, filamentous hemagglutinin (FHA) and hepatitis B surface antigen (HBsAg) will be measured by an in-house Luminex multiplex immunoassay. Immune responses to the primary series of PCV will be measured by a standardized enzyme immunoassay (EIA) to test for vaccine serotype-specific capsular immunoglobulin (Ig) G antibody concentrations and opsonophagocytic assay. Titres of rotavirus-specific IgA will be determined in enzyme-linked immunosorbent assays. Refer to appendix 10 for the serological correlates of protection .

**Sample size:** The anticipated prevalence of neurological sequelae in CMV uninfected controls with uneventful foetal or perinatal periods is estimated at 1%. Prevalence of neurological sequelae in CMV infected infants is expected to be higher at approximately 17%. For 80% power, the difference that could feasibly be detected, is 17-fold i.e. 1% vs 17%. Allowing for a loss to follow up of 10%, 42 CMV infected infants and 84 controls (n=126) with an allocation ratio of 1:2 are required ([Appendix 9](#)).

**Data Analysis:** Table 3 describes the data analysis plan to determine the incidence and risk factors for neurological sequelae in congenital CMV infected infants

Table 3: Data analysis plan

Objective 3  Incidence calculation of one or more neurological sequelae for cases and controls at 2 weeks, 2 months, 6 months and 12 months of age dependent on investigations done at each visit  Comparison of proportions with permanent sequelae (hearing impairment and developmental deficit) at each visit between cases and controls using a Z test to compare ratios, including 95% confidence intervals.  Adjust for potential confounders (IUGR, symptoms at birth, gender and co-morbidities) by multiple logistic regression analysis to establish factors contributing to neurological sequelae.
Objective 6  Incidence of postnatal acquisition of CMV in newborns will be calculated at 2 months, 6 months and 1 year of chronological age. Incidence of neurological sequelae in postnatally infected infants will be calculated
Objective 7

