The magnitude of specific antibody response between cases and controls will be compared using the unpaired t test when data are normally distributed. In the scenario that the distribution is non-normal the Mann-Whitney test will be used instead. Normality will be tested using the Shapiro-Wilk test, where the assumption of non-normal data will be concluded based on a significant result. Frequency plots and P-P plots will also be used to confirm the normality assumption, or not.

Simple correlations will be assessed using Pearson or Spearman correlation in the case of normal or non-normal distribution, respectively. The resulting correlation coefficient will indicate the strength of association, whereas the significance test will provide the evidence of a linear correlation or not in the population.

**Potential challenges:** To account for loss to follow up and timely completion of investigations, a window period of 30 days is allowed from the date of each scheduled visit in which to perform the investigations. Transport costs will be reimbursed with R150 per scheduled visit and all investigations will be provided at no cost. Neurological sequelae in congenital CMV infected children may manifest beyond 12 months of age and long term follow up to 6 years is recommended. Hence, it is possible that this study may not detect all sequelae by 12 months of age and no differences may be observed between the 2 groups.

Parents may be reluctant to consent to a blood draw at 6 months of age and will be thoroughly counselled on the purpose and processing of the blood samples. The informed consent form has been amended to include the purpose of the blood draw and each mother will be given a new consent form to sign with the option of refusing to participate in the blood draw but continue with the rest of the study procedures.

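### Objective 7 correlations: the test is described as evidence on linear correlation for Spearman as well as Pearson, and a non-significant result can be read as no correlation because no confidence interval is planned

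*Combined protocol and SAP*

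**What the plan says.** The text under Objective 7 in Section 3.4 (Data Analysis) first sets a rule for judging normality: "Normality will be tested using the Shapiro-Wilk test, where the assumption of non-normal data will be concluded based on a significant result". Frequency and P-P plots support that judgement. It then chooses the correlation method: "Simple correlations will be assessed using Pearson or Spearman correlation in the case of normal or non-normal distribution, respectively". The interpretation follows in one sentence with two halves. The first is "The resulting correlation coefficient will indicate the strength of association". The second is "the significance test will provide the evidence of a linear correlation or not in the population". Both halves apply to whichever coefficient was chosen.

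This part of the plan gives no confidence interval for the coefficient, no smallest correlation of interest and no significance level. It does not say which variables are to be correlated, or in which infants.

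The cohort size is set in Section 3.4 (Sample size) for neurological sequelae under Objective 3, at 1% against 17% with 80% power: "42 CMV infected infants and 84 controls (n=126) with an allocation ratio of 1:2 are required". That figure includes a 10% allowance for loss to follow-up. Mothers are also offered a consent form for the 6-month blood sample "with the option of refusing to participate in the blood draw but continue with the rest of the study procedures". Section 2.2 lists Objective 7 as exploratory.

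**The concern.** The sentence has two faults of interpretation.

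- **The word linear.** Spearman's coefficient is computed on ranks. A significant result supports a monotone relation, which may be far from a straight line. The plan sends any measure judged non-normal to Spearman, so the description is wrong for one of the two methods it covers.
- **The words that give the test a role in showing absence.** A non-significant test means only that the data did not exclude zero. Whether they also exclude correlations worth knowing about depends on the width of the interval, and no interval is planned.

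What is at stake is how a null correlation is read. Section 1.2 notes that only a few groups have studied CMV and infant vaccine responses in children, so a null result from this cohort could carry weight. The point estimate alone does not show how much uncertainty surrounds it.

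**Working it through.** The plan states no power or detectable coefficient for the correlations, so there is no figure of its own to reproduce. The check has two parts.

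**1. Does a Spearman test speak to linearity?** Take y = exp(x) at 40 points from x = 0.1 to 10. Spearman's coefficient is 1.00 and Pearson's is 0.69. The rank correlation is perfect although the relation is strongly curved, so a significant Spearman result cannot be read as evidence of linearity. This part needs no assumption about sample size.

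**2. How informative is a non-significant result?**

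Inputs:
- Cohort: 42 cases and 84 controls (Section 3.4, Sample size).
- Loss to follow-up: 10% (same place). 42 × 0.9 = 37.8, about 38 cases. 84 × 0.9 = 75.6, about 76 controls. 38 + 76 = 114 infants.
- Significance level: two-sided 5%. This is an assumption. It matches the 95% intervals planned for Objective 3.
- Refusal of the blood draw: no rate is given, so none is applied. Any refusal lowers n.

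Formulas (Fisher z):
- Smallest significant |r| = tanh(1.96 / √(n − 3))
- Power at true ρ = Φ(atanh(ρ) × √(n − 3) − 1.96)
- True ρ with 80% power = tanh((1.96 + 0.84) / √(n − 3))

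Worked for 38 cases, with √35 = 5.916:
- Smallest significant |r| = tanh(1.96 / 5.916) = tanh(0.331) = 0.32.
- Power at ρ = 0.3: atanh(0.3) = 0.3095. 0.3095 × 5.916 = 1.831. Φ(1.831 − 1.96) = Φ(−0.129) = 45%.

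Worked for 114 infants, with √111 = 10.536:
- Smallest significant |r| = tanh(1.96 / 10.536) = tanh(0.186) = 0.18.
- Power at ρ = 0.3: 0.3095 × 10.536 = 3.261. Φ(3.261 − 1.96) = Φ(1.301) = 90%.

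| Infants analysed | n | Smallest significant \|r\| | Power at ρ = 0.2 | Power at ρ = 0.3 | Power at ρ = 0.4 | ρ with 80% power |
|---|---|---|---|---|---|---|
| Cases only | 38 | 0.32 | 22% | 45% | 71% | 0.44 |
| Controls only | 76 | 0.23 | 41% | 75% | 95% | 0.32 |
| All evaluable | 114 | 0.18 | 57% | 90% | 99% | 0.26 |

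These are Pearson figures. For Spearman, with the variance taken as 1.06/(n − 3), the correlation with 80% power rises slightly, to 0.45 in 38 cases and 0.27 in 114 infants.

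**What an interval would show.** Suppose r = 0.25 is observed in 38 cases. It is below 0.32 and so not significant. On the z scale, atanh(0.25) = 0.255, and 0.255 ± 0.331 gives −0.076 to 0.587. Back-transformed, the 95% interval is −0.08 to 0.53. That result is compatible with no correlation and with a substantial one. If r = 0 were observed, the interval would be −0.32 to 0.32 in 38 cases and −0.18 to 0.18 in 114 infants.

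**The case against.** The best defence is that the sentence is an ordinary, loosely worded account of what a test is for. It speaks of providing evidence and sets no threshold. It also begins by giving the coefficient as the strength of association, so a reader of the results would see the estimate beside the test. The authors separate Pearson from Spearman in the sentence before. They acknowledge limits on null findings elsewhere: low power for stratifying by HIV in the Objective 5 analysis (Section 3.3, Table 3), and sequelae that may appear only after 12 months (Section 3.4, Potential challenges). The main Objective 7 comparison is antibody magnitude between groups, with correlations as an addition.

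Much of this stands, and it rules out several stronger readings that a reader might infer:

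- **That the plan lets the test decide, and that p > 0.05 will be reported as no correlation.** The text contains no such rule.
- **That a true correlation of 0.3 would be missed 55% of the time (100 − 45).** This needs a cases-only analysis at a two-sided 5% level, and the plan states neither. In all evaluable infants the figure is about 10%.
- **That a curved relation found by Spearman will be reported as linear.** The wording permits this but does not show that it will happen.
- **That the cohort should have been sized for correlations.** An exploratory objective does not require that.

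The defence does not rescue the sentence itself. Linear remains wrong for Spearman. A point estimate without an interval does not tell the reader what a null result rules out. The caveats elsewhere concern other objectives.

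**Conclusion.** The point holds as a minor fault of interpretation in an exploratory analysis. The error about linearity is certain and rests on no assumption. The second fault is that the wording allows a non-significant result to stand as evidence of absence, with no interval planned to guard against it.

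How much the second fault matters depends on choices the plan leaves open. Under a two-sided 5% level and 10% loss, a null result says little in a cases-only analysis and considerably more in the whole evaluable cohort, at least for correlations of 0.3 or larger. Refused blood draws would weaken both by an amount that cannot be calculated from the documents. Appendix 3, which summarises the analyses, was not in the text available.

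The documents do not support a claim that false reports of no correlation are planned, or that they would occur at any particular rate. Nor does this fault require separate coefficients for cases and controls.

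**What to change.** In Section 3.4, Data Analysis, Objective 7, keep the coefficient as the measure of strength and replace the sentence on its interpretation with:

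> Each coefficient will be reported with its 95% confidence interval; Pearson will be interpreted as linear and Spearman as monotone association; a non-significant result will not be interpreted as absence of correlation.

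The cost is one sentence of analysis text and one extra line of output per coefficient. It needs no further infants, samples or visits, and leaves the choice between Pearson and Spearman as it is.

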### 3.5 Objective 4 Methods

**Study design:** This study will be nested within a broader study conducting Minimally Invasive Tissue Sampling (MITS) on death of children and stillbirths currently underway in CHBAH,

ongoing until end 2017 (HREC no. 150215), and includes testing for CMV. I perform MITS in this study and will be involved in data analysis as it relates to CMV and neonatal deaths or stillbirths.

**Study participants:** Stillbirths weighing  $\geq 1000\text{g}$  and neonatal deaths weighing  $\geq 750\text{g}$ , less than 3 weeks of age from non-traumatic causes at CHBAH. Parents/guardians provide written consent after death, following grief counselling and provision of an information leaflet.

**Data collection:** Ante-mortem clinical data will be extracted from patient records in the BoSS CRF ([Appendix 6](#)). Core biopsy specimens of lung, liver, kidney, brain tissue, placenta (stillbirths) and fluid specimens of cerebrospinal fluid (CSF) and blood will be sampled from each enrolled case within 72 hours of birth.

**Sample size:** This will be a descriptive study, and sample size is based on the number of deaths/stillbirths which occur over a 18-24 month period. From current experience, we anticipate enrolling approximately 200 stillbirths and 100 neonatal deaths, providing 80% precision to determine that at least 5% of these stillbirths and neonatal deaths are associated with CMV.

**Laboratory:** Testing and examination for CMV infection by histopathological methods will take place at the National Health Laboratory Services (NHLs). Molecular testing (PCR) will occur at the RMPRU laboratory by in house assays. HIV PCR and antibody ELISA will be done to determine infection and exposure *in utero* as has been approved in the parent protocol (HREC no. 150215). Refer to [Appendix 13](#) for the full tissue sampling protocol of the study.

**Data analysis:** Descriptive statistics presenting the number of deaths with CMV infection by birthweight, gestational age at birth and age at death in neonates. Multiple regression analysis will adjust for confounding factors such as HIV infection and exposure, prematurity, co-morbidity and co-infection with other pathogens. The odds of CMV disease will be compared to

the prevalence of congenital CMV in the general population, stratified by HIV-exposure status, as measured in Objective 2.

**Study challenges:** Although the majority (75%) of parents approached thus far, consent to the procedure, enrolment of neonatal deaths has been limited due to cultural practices of burying neonates immediately after death before study staff are able to approach the parents for consent. In contrast, we are enrolling approximately 5 stillbirths per week. This challenge will be mitigated by engaging with attending paediatricians to inform the study team more timeously if deaths occur. MITS in aborted foetuses is not being done in the current study but is an important demographic in describing the outcomes of congenital CMV infection.

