### **2.1 Primary Objectives:**

2. 1. Determine the CMV seroprevalence, antibody avidity and (if possible) anti-CMV neutralising antibody activity in blood plasma of both HIV infected and uninfected pregnant women at the time of delivery and explore associations between these measures and risk of congenital and postnatally acquired CMV infection in the first year of life. To compare the prevalence of congenital CMV infection and incidence of symptomatic infection in HIV-exposed and HIV-unexposed neonates

3. To determine the incidence and risk factors for neurological sequelae in congenitally CMV infected neonates from birth up to 12 months of age compared to a control group of neonates without congenital CMV
4. To determine by minimally invasive tissue sampling (MITS) the association between congenital CMV infection and: 1) Neonatal deaths less than 3 weeks of age and 2) Stillbirths

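### Objective 4: the tissue-sampling window, counted from birth, contradicts the three-week age limit for neonatal deaths

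*Combined protocol and SAP*

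**What the plan says.** All of this is in the combined protocol and SAP.

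- **Objective.** Section 2.1, Objective 4, asks about the association of congenital CMV with stillbirths and with "Neonatal deaths less than 3 weeks of age".
- **Eligibility.** Section 3.5, Study participants, repeats the limit: neonatal deaths "less than 3 weeks of age from non-traumatic causes at CHBAH".
- **Consent.** The same paragraph says "Parents/guardians provide written consent after death", so tissue is taken post-mortem.
- **Sampling window.** Section 3.5, Data collection, says that biopsy and fluid specimens "will be sampled from each enrolled case within 72 hours of birth".
- **Planned numbers.** Section 3.5, Sample size, expects "approximately 200 stillbirths and 100 neonatal deaths", a forecast based on experience in the running study.
- **Analysis.** Section 3.5, Data analysis, will describe CMV-infected deaths by, among other things, "age at death in neonates".
- **Fuller procedure.** Section 3.5, Laboratory, points to Appendix 13 "for the full tissue sampling protocol of the study". That appendix is not in the text available for review.

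**The concern.** The eligibility rule and the sampling rule sit in consecutive paragraphs and run on different clocks. Eligibility is set by age at death and extends to three weeks. Sampling is limited by time since birth and ends at three days. The sampling sentence covers every enrolled case and makes no separate provision for neonatal deaths. No window counted from death appears anywhere in the available text.

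If staff follow the sentence, the neonatal arm becomes a sample of deaths in the first three days. Objective 4 is framed for deaths under three weeks, and such a sample could not answer it. The selection would also carry into the planned comparison with the population prevalence of congenital CMV from Objective 2. If staff instead sample later deaths, each of those samples falls outside the written rule, and whether it enters the analysis would be decided after the event.

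**Working it through.** The plan gives no figure for this point that could be reproduced. The check is a comparison of two time windows.

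**Inputs (sections 2.1 and 3.5)**
- D = age at death of a liveborn infant. Eligibility requires D < 3 weeks = 21 days.
- S = age at sampling. The sampling rule requires S ≤ 72 hours = 72/24 = 3 days.
- Consent comes after death and sampling is post-mortem, so S ≥ D.

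**Neonatal deaths**
1. From D ≤ S and S ≤ 3 days, D ≤ 3 days.
2. Eligible age range: 21 days. Part of it that can satisfy the sampling rule: 3 days.
3. Overlap: 3/21 = 14.3% of the age range. Remainder: 18/21 = 85.7%.
4. Example: an infant who dies on day 10 is eligible, but the sampling window closed 10 − 3 = 7 days earlier.
5. An infant who dies shortly before 72 hours can be sampled only if consent and the procedure fit into the time left, so 3 days is an upper bound.

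The percentages in step 3 are shares of the age range, not of deaths. Deaths need not be spread evenly over the three weeks, and the documents give no distribution.

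**Stillbirths**

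Delivery starts the clock and the infant is already dead, so a window of 72 hours from birth can be met. About 200 of 200 + 100 = 300 planned cases, or two thirds, are unaffected.

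**Analysis by age at death**

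Under a literal reading, every cell of that description beyond day 3 is empty, because no such death could have been sampled within the rule.

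**What a smaller neonatal arm would mean for precision**

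This step is conditional and does not estimate the loss. It uses the 5% proportion in the sample-size statement and a 95% half-width of 1.96 × √(0.05 × 0.95 / n).

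| Neonatal deaths sampled (n) | Source of n | 95% half-width |
|---|---|---|
| 100 | plan's forecast | ±4.3 points |
| 90 | assumption, upper end | ±4.5 points |
| 25 | assumption, lower end | ±8.5 points |

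The plan's own statement of 80% precision cannot serve as a benchmark, because it names neither a half-width nor a reference proportion.

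**The case against.** **This is probably a wording slip.** Consent after death, analysis by age at death, and the difficulty in section 3.5 (Study challenges) of burial before parents can be approached all describe work triggered by a death. Counting from birth suits the stillbirths, who make up most of the sample, and may have been carried over to the neonates. This is plausible. It makes the point an inconsistency of wording rather than a deliberate design choice, but the sentence is still an operative methods rule and needs correcting.

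**Another document may govern sampling.** Objective 4 is nested in an approved study already under way, and Appendix 13 is cited for the full procedure. It may state a workable window. This stands as a limit on the finding: confidence is high for the contradiction in the text, not for what happens in practice. If Appendix 13 differs, this section still has to match it.

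**Birth may have been intended, to support attribution to congenital infection.** Section 1.2 puts the diagnostic limit for congenital infection at two weeks of life, so it does not explain 72 hours. If birth was deliberate, the three-week eligibility is the part that conflicts.

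**Stronger readings that the documents do not support**
- *A definite number of the 100 neonatal deaths would be lost, or the 100 could not be reached.* With no age-at-death distribution, any count rests on assumption. The 100 is also a forecast from current experience, so it may already reflect whatever window the running study uses.
- *Nothing limits the time from death to sampling.* For a liveborn infant who meets the rule, death cannot precede birth, so the interval is at most 72 hours.
- *Later deaths are not being sampled.* The text does not show this.

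**Conclusion.** The contradiction is real as written and nothing in the available text resolves it. It concerns the neonatal-death arm only, about 100 of 300 planned cases. Read literally, sampling is possible for deaths in at most the first 3 of 21 eligible days of age. That would confine the arm to very early deaths, leave Objective 4 unanswered for the rest of the three weeks, and empty the age-at-death description after day 3.

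The conclusion rests on two readings: that sampling cannot precede death, which the consent rule implies, and that the sentence covers neonatal deaths, as its reference to every enrolled case indicates. It does not rest on any assumed age-at-death distribution. Objective 4 is a primary objective, though its component study is described as descriptive. The point is worth settling because it costs little and decides in advance which samples count.

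**What to change.** Reconcile the sampling window in section 3.5 (Data collection) with the age limit in section 3.5 (Study participants) and Objective 4, and with the parent tissue-sampling protocol in Appendix 13. State the start point separately: delivery for stillbirths, and death rather than birth for neonatal deaths. Take the length of the window from the parent protocol; it should not be assumed that 72 hours carries over to the new start point. If the parent protocol does count from birth for neonates, the eligibility rule and Objective 4 must instead be brought into line with it.

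The cost is about one line of protocol text and a check against Appendix 13. Aligning the text with the parent protocol needs no extra staff or procedure.

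### Objective 4 sets CMV disease in decedents against CMV infection in live births, gives no body-text rule for CMV found in deaths at days 14–20, and leaves its 80% precision undefined

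*Combined protocol and SAP*

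**What the plan says.** All references are to the combined protocol and SAP.

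- **Objective.** Section 2.1 lists, as a primary objective, the association of congenital CMV infection with stillbirth and with "Neonatal deaths less than 3 weeks of age".
- **Comparison.** The measure in decedents is given in section 3.5, Data analysis, by the words "The odds of CMV disease will be compared to", and the comparator named there is "the prevalence of congenital CMV in the general population, stratified by HIV-exposure status, as measured in Objective 2". A multiple regression is also planned.
- **Same section, other wording.** The Laboratory paragraph says "Testing and examination for CMV infection by histopathological methods will take place" and adds PCR. The descriptive analysis is "Descriptive statistics presenting the number of deaths with CMV infection by birthweight, gestational age at birth and age at death in neonates".
- **Sample size.** Section 3.5 calls the study descriptive, with numbers set by expected enrolment: about 200 stillbirths and 100 neonatal deaths, "providing 80% precision to determine that at least 5% of these stillbirths and neonatal deaths are associated with CMV".
- **Sampling.** Tissue and fluids "will be sampled from each enrolled case within 72 hours of birth".
- **Appendix.** Section 3.5 refers to Appendix 13 "for the full tissue sampling protocol of the study". Appendix 13 and Appendix 11 (case definitions) are not in the text available for review.

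**The concern.** Three features of a primary objective could each change what it reports.

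1. **Unlike quantities.** Disease is set against infection. Section 3.5 plans both histopathology and PCR and does not define CMV disease, so an analyst could code either as the outcome. If only diseased decedents count while every infected live birth counts, the association with death is understated.
2. **Third-week deaths.** Section 1.2 treats a positive specimen as diagnostic of congenital CMV only in the first 2 weeks of life, yet eligibility runs to 3 weeks. CMV acquired at or after delivery could then be counted as congenital.
3. **Undefined precision.** Without a confidence level, width, reference rate or test, a reader cannot tell what 200 stillbirths and 100 neonatal deaths can show, least of all within the HIV strata that the plan will compare.

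**Working it through.** **Inputs.** Section 3.5: n = 200 stillbirths and 100 neonatal deaths (300 together), target 5%. Section 3.3, Objective 2 sample size: 2.9% in 1077 HIV-exposed and 1.0% in 1077 unexposed infants. So the comparator has 1077 + 1077 = 2154 infants at (2.9 + 1.0)/2 = 1.95%. Section 1.2: 29.9% HIV prevalence in pregnant women.

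**The plan's figure.** The 80% cannot be reproduced, because no formula or inputs are given. Objective 1, in section 3.3, states both a 5% precision and a 95% confidence level. Readings tried, at p = 5%:

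- Wald 95% half-width, 1.96 × √(0.05 × 0.95/n).
- The same as a share of 5%.
- Exact (Clopper–Pearson) 95% interval at an observed 5%.
- Two-sided 5% power against 1.95% in 2154: Φ[(0.05 − 0.0195 − 1.96 × SE₀)/SE₁]. SE₀ uses the pooled proportion and SE₁ the separate ones.

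| n | half-width (points) | relative | exact 95% CI | power |
|---|---|---|---|---|
| 100 | 4.3 | 85% | 1.6–11.3% (5/100) | 53% |
| 200 | 3.0 | 60% | 2.4–9.0% (10/200) | 72% |
| 300 | 2.5 | 49% | 2.8–8.1% (15/300) | 83% |

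Power at n = 200 in full:

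- Pooled p = (10 + 42.0)/2354 = 0.0221
- SE₀ = √[0.0221 × 0.9779 × (1/200 + 1/2154)] = 0.01087
- SE₁ = √[0.05 × 0.95/200 + 0.0195 × 0.9805/2154] = 0.01570
- (0.0305 − 1.96 × 0.01087)/0.01570 = 0.586, and Φ = 0.72

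The chance of at least one case is 99.4% or more at every n, and the chance of observing 5% or more is 54–56%. None of the precision readings gives 80%. Some power readings come close: one-sided power against 1.95% at n = 200 is 79%, and one-sided power against 1.0% in 1077 at n = 100 is 82%. Each needs a reference rate and a test that the plan does not state.

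**HIV strata.** Assume 29.9% of decedents are exposed. Then 0.299 × 200 ≈ 60 stillbirths are exposed and 140 are not. Exact 95% intervals at 5% are 1.0–13.9% (3/60) and 2.0–10.0% (7/140).

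**Disease against infection.** Suppose 5% of decedents are infected, the comparator is 1.95%, and a share f of infected decedents is called diseased. The documents do not give f; assume 0.25 to 1. The odds ratio is [0.05f/(1 − 0.05f)] ÷ (0.0195/0.9805).

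| f | counted | odds ratio |
|---|---|---|
| 1 | 5.0% | 2.65 |
| 0.75 | 3.75% | 1.96 |
| 0.5 | 2.5% | 1.29 |
| 0.25 | 1.25% | 0.64 |

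This shows direction only. Comparing an odds with a prevalence matters little here: the odds at 5% are 0.05/0.95 = 0.0526.

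**Third-week deaths.** No age-at-death distribution is given. Assume 5–20% of the 100 neonatal deaths fall at days 14–20 and 10–30% of those carry CMV acquired at or after birth. The extra positives run from 100 × 0.05 × 0.10 = 0.5 to 100 × 0.20 × 0.30 = 6, against 5 expected at 5%. Both ranges are assumptions.

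**Sampling window.** Read literally, sampling within 72 hours of birth cannot be met for a death after day 3, yet deaths under 3 weeks are eligible.

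**The case against.** The strongest reply is that these are clarifications. The objective, the laboratory paragraph and the descriptive analysis all say infection, and only one sentence says disease. That is fair, so the bias is conditional on a literal reading. A reader might go further and apply the 85–90% asymptomatic share from section 1.2 to decedents, inferring an odds ratio of about 0.10–0.15 under no association. The documents do not support that: the share describes infected newborns at birth, not infected stillbirths or neonates who died.

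The third-week problem is narrow. Stillbirths, the larger group, are unaffected, age at death is tabulated, and an appendix may hold a rule. A reader might also infer that decedents lack the breast-milk safeguard used for live births. That safeguard addresses contamination of a mouth swab, so it does not carry over directly to biopsies, CSF and blood. Section 1.2 also lists tissue and blood beside saliva and urine as diagnostic specimens, so the specimen difference is a limitation, not an error.

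On precision, the study is called descriptive and its size follows enrolment, so no design decision depends on the 80%. That stands too. But a regression and an HIV-stratified comparison are also planned, and a descriptive study still needs a defined precision.

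**Conclusion.** The point holds as three corrections to a primary objective, plus one wording conflict.

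1. The disease/infection mismatch is probably loose wording. If applied literally, and if disease is counted only among the infected, the ratio is biased downward by an amount that cannot be calculated from the documents.
2. The body text has no rule for classifying CMV in deaths at days 14–20. The effect is confined to that part of about 100 neonatal deaths and its size is unknown.
3. The 80% precision is undefined. It is tempting to call it wrong, or to call the study underpowered. The documents support neither: depending on the group, reference rate and test chosen, power falls on either side of 80%, and the pooled 300 give 83% against 1.95%.

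The 72-hour wording and the under-3-weeks eligibility contradict each other and must be reconciled. A reader might also set about 5 stillbirths per week (section 3.5, Study challenges) against the forecast of 200: 5 × 78 = 390 to 5 × 104 = 520 over 18–24 months. That is a minor planning matter, since the rate may not last, and it is not part of this conclusion.

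**What to change.** - **Outcome.** Use PCR-detected CMV infection in decedents and in Objective 2 live births, both for the HIV-stratified odds ratio and for the regression. Report histological CMV disease separately. State the tissue-versus-saliva/urine difference as a limitation.
- **Age.** Keep all deaths under 3 weeks in the descriptive tables. Restrict the congenital-CMV comparison to stillbirths and neonatal deaths at under 14 days of age, judged by age at death and not by sampling date, and report later deaths separately. If an appendix already has a rule, cite it in section 3.5 instead.
- **Precision.** Replace the 80% with expected exact 95% intervals at an observed 5%: 2.4–9.0% (10/200), 1.6–11.3% (5/100) and 2.8–8.1% (15/300). State that the HIV strata will be wider, for example 1.0–13.9% for 3/60 if 29.9% of decedents are exposed.
- **Sampling window.** Reconcile the 72-hour wording with the eligible age range.

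The cost is wording and one analysis definition, since PCR, histopathology and age at death are already planned. The congenital comparison will have slightly fewer neonatal deaths, and the specimen difference remains.
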